#### **Objectives**

- To describe patients, invasive procedures, infections, and antimicrobials prescribed.
- To estimate the prevalence of clinical isolates from ICU patients that are positive for carbapenemase-producing Enterobacterales.
- To estimate the prevalence of rectal screening isolates from ICU patients that are positive for carbapenemase-producing *Enterobacterales*.
- To understand patient characteristics, procedures, and antimicrobial use which are associated with CPE colonisation or infection
- To understand inequalities in the prevalence of CPE colonisation and infection.
- To raise awareness of the growing concern of CPE in ICU patients.

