# **Data analysis**

For hospital, ward and patient demographic variables, descriptive and summary statistics will be presented. CPE prevalence estimates will be calculated overall and also presented by strata. Associations between colonisation or infection with CPE and hypothesised risk factors data will also be analysed using univariable, and if required, multivariable analysis. Results will be stratified by ICU-type, with odds ratios, p-values and 95% CI. All analysis will be done using Stata 15.1.

Anonymised results from the survey may be used to inform additional CPE/CPO assessments to understand the impacts of AMR in line with the National Action Plan.

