#### The following data will be collected once per patient

The following data should be answered in relation to the date as referenced in the list below.

Note only one date is required, please complete for the first that is applicable as working down the list

- 1. Date of screening test (if single test)
- 2. If multiple screening tests:
  - a. If any positive, date of first positive screen OR
  - b. If all negative, date of most recent screen
- 3. Today's date if never screened

Field name	Field description	Response/notes				
Patient details						
Patient ID	Unique patient ID	System generated				
*Reporting organisation	ICU name	Single select drop down				
*Date of interest	Date of interest to which exposure questions relate. In order of preference:	DD-MM-YYYY				
	1. Date of CPE screening test (if single test) 2. If multiple CPE screening tests: a. If any positive, date of first positive screen OR b. If all negative, date of most recent screen					
	3. Today's date if never screened					
*10-digit NHS number	10-digit NHS number, if not available, enter [contact]					
*Forename	Patient first name	Text				
*Surname	Patient surname	Text				
*Date of birth	Patient date of birth	DD-MM-YYYY, if not known enter 01/01/1900				
*Sex	Biological sex	Button options:				
		Male Female Unknown				
Patient details 2						
*Survey date	Date survey is conducted	DD-MM-YYYY				
*Patient age group		Single select drop-down: Adults				
		Paediatrics				
		Neonates				

Ethnicity	Ethnicity of patient	Two-stage single select drop-down
*UK resident	Indicate if patient normally resides in the UK  NB. If for a neonate, please use details of mother	Single select drop-down: Yes No Unknown
Normal country of residence if not UK		Single select drop-down
*Birthweight	Birth weight (in grams) of neonatal patients i.e. babies less than 28 days old OR on NICU.	Number in grams
*Gestation	Gestation for babies aged under 1 year	Weeks + days
*Patient category	Indicate patient category on admission	Single select drop-down: NHS Private Diplomatic Other Unknown
Other patient category	Specify patient category if "other"	Text
*Date admitted to hospital	Date admitted to the trust, or date of birth if neonate and admitted since birth	DD-MM-YYYY
*Admitted from	Setting patient admitted from into the trust	Single select drop-down:  Home  A&E International transfer Nursing home Other Trust  Non-NHS hospital Non-health-related institute Temporary accommodation Other

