Indicate which carbapenemase family was detected (select all that apply)	Indicate which carbapenemase family was detected (select all that apply)	Multiselect drop-down
If Other, specify other carbapenemase family		Text
Screening (NB no additional sc	reening is required)	
*CPE on admission to Trust	Was the patient known to be CPE positive on admission to Trust	Single select drop-down: Yes – colonised Yes - infected No Unknown
*CPE screening on admission to Trust	Found to be CPE positive on admission to Trust.  "Yes" if screening specimen positive, "no" if screening specimen negative, "unknown" if no screen performed.	Single select drop-down: Yes No Unknown
*CPE on admission to ICU	Known to be CPE positive on this admission to ICU i.e. communicated/identified at time of admission.	Single select drop-down: Yes No Unknown
*ICU screen required	Did patient meet requirement to be screened for CPE on ICU in accordance with your policy?	Single select drop-down: Yes No Unknown
*ICU admission screen	Was patient screened for CPE on this admission to ICU?	Single select drop-down: Yes No Unknown

		1
*ICU admission screen date	Date admission screen was taken on ICU	DD-MM-YYYY
*Result of ICU admission screen	Indicate result from ICU CPE admission screen	Single select drop-down: Positive Negative Unknown
*Previous CPE	Indicate if patient known to be CPE colonised/infected in 12 months prior to first day of survey	Single select drop-down: Yes – colonised Yes - infected No Unknown
If previous history of CPE, specify date of most recent positive result.	Provide date of most recent CPE positive result (prior to ICU admission screen, if taken)	DD-MM-YYYY
Previous contact with CPE	Indicate if in contact with known CPE case during this admission	Single select drop-down: Yes No Unknown
Healthcare exposure		
*UK non-NHS hospital admission in previous 12 months	Any hospital admissions to non-NHS hospitals in the previous 12 months	Single select drop-down: Yes No Unknown
Specify UK non-NHS hospital admission	Provide name(s) of non- NHS hospitals admitted to in previous 12 months	Free text
*Healthcare overseas in previous 12 months	Any hospital admissions overseas in 12 months prior to admission at Trust	Single select drop-down: Yes No Unknown
Specify healthcare abroad	List countries where overseas healthcare received in previous 12 months	Multiselect dropdown of countries

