*Healthcare worker  Travel exposure	Includes working in hospitals, care/nursing homes, hospices	Single select drop-down: Yes No Unknown
*Overseas travel in previous 12 months (if known)	Any overseas travel in 12 months prior to admission to Trust	Single select drop-down: Yes No Unknown
*Specify overseas travel	List countries travelled to in previous 12 months	Multiselect dropdown of countries
Family travel	Any family members within the same household as patient travel in the previous 12 months	Single select drop-down: Yes No Unknown
Specify family travel	List countries where family members travelled in previous 12 months	Multiselect dropdown of countries
Interventions		
*Has the patient undergone major surgery since admission to the Trust, on or prior to the date of interest?	Surgery is defined as a procedure where an incision is made (not just a needle puncture), with breach of mucosa and/or skin (not necessarily in an operating theatre). If the patient has had more than one surgery since admission, report the most recent surgery.	Single select drop-down: Yes No Unknown
*Surgery date	If yes, date of surgery	DD-MM-YYYY
*Has the patient undergone endoscopy since admission to the Trust, on or prior to the date of interest?	If yes, surgery type Undergone endoscopy during this admission, prior to date of interest	Free text  Single select drop-down:  Yes  No Unknown

*Endoscopy date	If yes, date of most recent endoscopy	DD-MM-YYYY
Endoscopy type	If yes, specify type of endoscopy	Single select drop-down:  Colonoscopy Sigmoidoscopy Upper endoscopy/ Esophagogastroduodenosc opy (EGD) Endoscopic retrograde cholangiopancreatography (ERCP) Percutaneous endoscopic gastrostomy (PEG) Other
*Is the patient currently receiving Chemotherapy	Is the patient currently receiving chemotherapy for cancer treatment, or received chemotherapy in the four weeks prior to the date of interest	Single select drop-down: Yes No Unknown
Specify chemotherapy indication (select all that apply)		Single select drop-down:  Oral, nasal and pharyngeal Oesophagus Stomach Colorectal Hepatobiliary Respiratory Larynx Lung Breast Female reproductive Prostate Testicular Renal Urinary bladder Bone and joint Melanoma Non-melanoma skin Soft-tissue sarcoma Brain Leukaemia (other than

		chronic B-cell leukaemia) Chronic lymphocytic (including hairy cell leukaemia) Other
Chemotherapy indication if other		Free text

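### For babies in the trust since birth, the two mandatory overseas questions cover only time before birth, and no mother-as-proxy instruction is attached to them

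*Protocol*

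**What the plan says.** The per-patient part of Appendix 1 of the protocol has four yes/no questions on healthcare and travel over 12 months. Two of them, both starred as mandatory, look back from trust admission:

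- overseas healthcare: "Any hospital admissions overseas in 12 months prior to admission at Trust"
- overseas travel: "Any overseas travel in 12 months prior to admission to Trust"

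The other two have no such anchor. UK non-NHS admission, also starred, asks about "Any hospital admissions to non-NHS hospitals in the previous 12 months". Family travel, not starred, asks about "Any family members within the same household as patient travel in the previous 12 months".

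The hospital admission field defines the anchor date: "Date admitted to the trust, or date of birth if neonate and admitted since birth". The UK residence field carries the only instruction to answer for the mother: "NB. If for a neonate, please use details of mother".

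One of the Objectives is "To understand patient characteristics, procedures, and antimicrobial use which are associated with CPE colonisation or infection". Under Data analysis, the protocol says "Results will be stratified by ICU-type, with odds ratios, p-values and 95% CI".

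**The concern.** Neonates are one of three separately sized groups, and associations are to be reported by ICU type. A baby who has never left hospital can have an overseas exposure only through the mother or household. The form recognises this for residence but not for the two overseas items. Read literally, those items ask a newborn about a year in which it was not yet born.

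Two outcomes are possible. If staff follow the wording, every such baby is No or Unknown and the exposure does not vary. If some staff carry the mother rule over from the residence field and others do not, the same answer means different things in different trusts, and the data set does not show which was meant. A baby of a mother who lives abroad could be recorded as not UK resident and, in the same record, as having no overseas travel.

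The protocol's Background describes some countries as close to endemic for these organisms, so overseas exposure is a natural candidate for the association objective. Data never asked for cannot be recovered in the analysis. Linkage is an unlikely rescue: under Information collected, the protocol says that items reliably available by linkage have already been taken out of the questions.

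**Working it through.** **1. The window.** Let B be the date of birth and A the trust admission date. The two overseas items cover the interval from A minus 12 months to A. For a neonate admitted since birth the form sets A = B, so the interval runs from B minus 12 months to B. The patient's own time at risk in it is 0 days, and Yes is impossible.

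**2. Would the form's date of interest change this?** The per-patient section opens by tying answers to a date of interest (a screening date, or the survey date if never screened), although these two items name trust admission. Even if the later date governed, the added days would be days spent in hospital since birth. Overseas travel or an overseas admission still could not occur in them.

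**3. The four 12-month fields for a baby admitted since birth.**

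| Field | Mandatory | Window ends at | About | Can it be Yes? |
|---|---|---|---|---|
| Overseas healthcare | yes | trust admission = birth | patient | no, by construction |
| Overseas travel | yes | trust admission = birth | patient | no, by construction |
| UK non-NHS admission | yes | not tied to admission | patient | normally no, because of the continuous stay |
| Family travel | no | not tied to admission | household | yes |

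The anchor problem therefore affects two of the four fields. Neither of these two carries the mother note.

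**4. Effect on the odds ratio.** With a and b the exposed positives and negatives, and c and d the unexposed positives and negatives, OR = ad/(bc). In this subgroup a = b = 0, so the ratio is 0/0 and undefined.

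**5. How many positives are at stake.** The protocol's neonatal option 3 can be reproduced from its own inputs: N = 1441 beds, p = 0.01, d = 0.01, z = 1.96, design effect 2, plus 10% for non-completion.

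n = 2·N·p(1−p) / [(d/z)²·(N−1) + p(1−p)]
= 2 × 1441 × 0.0099 / [(0.01/1.96)² × 1440 + 0.0099] = 602.1, rounded up to 603.

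603 × 1.1 = 663.3, rounded up to 664, the stated figure.

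Expected positives among 603 completed records are 603 × 0.005 = 3.0 and 603 × 0.01 = 6.0.

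**6. Illustration with assumed shares.** The documents give neither the share of neonates admitted since birth nor the frequency of exposure. Assume 50-90% for the share, and 5-30% exposed (mothers, or the other neonates themselves).

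- As worded, exposed neonates come only from those not admitted since birth: from 603 × 0.10 × 0.05 = 3 to 603 × 0.50 × 0.30 = 90. This is generous, because a very young baby has had little time to travel.
- If all were admitted since birth, the count is 0.
- Answered for the mother: from 603 × 0.05 = 30 to 603 × 0.30 = 181.
- Exposed positives with maternal answers, at 1% prevalence and no association: from 0.3 (30.15 × 0.01) to 1.8 (180.9 × 0.01).

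The rewording restores variation in the exposure. It does not make a neonatal odds ratio precise.

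**The case against.** The strongest case against is that little is lost.

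- **The aim is untouched.** The main aim is a prevalence estimate, and that stands. With 3 to 6 expected positives, any neonatal association would be very imprecise however the items are worded. This is right, and it limits the weight of the point.
- **Family travel gives a route.** It can be Yes for a newborn, and a country list follows. This is right in part. The field is optional, does not single out the mother and does not ask about healthcare abroad.
- **Instructions may exist elsewhere.** The Training section promises written user guides, which are not shown and could tell staff to answer for the mother. That is possible, but the field descriptions are where the form gives this instruction for residence, and there it stops.
- **Not every neonate is affected.** Babies transferred in after birth are outside the argument. This is right.

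A reader might go further and infer that all the 12-month healthcare and travel questions fail for neonates; only two of the four use this anchor. UK non-NHS admission and healthcare worker will normally be a true No for such a baby, which is not an error in the form. The item on antibiotics in the past year but not the last four weeks is impossible only for babies under 28 days; the form's birthweight field also counts older babies on a neonatal unit as neonatal patients.

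A reader might also fear that neonates coded as unexposed would distort results for adults or children. The protocol plans to stratify by ICU type, so it does not support that fear. Nor is the problem as large as the whole neonatal group of 664 planned patients, because only babies admitted since birth are affected.

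**Conclusion.** The point holds for two mandatory fields, overseas healthcare and overseas travel, in neonates admitted since birth. It follows from the form's own definition of the admission date and needs no outside assumption. In that subgroup the two odds ratios cannot be estimated if staff follow the wording, and cannot be interpreted if staff differ in how they read it.

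The size of the subgroup is unknown, and the ranges in the illustration rest on assumed shares. The expected 3 to 6 positive neonates rest on the protocol's 0.5-1% prevalence and on 603 completed records. With so few, the gain is mainly descriptive: knowing whether the mothers of the positive babies had been abroad or in hospital abroad. The prevalence estimates and the adult and paediatric results are unaffected. This is a cheap improvement to the form, not a flaw in the survey design.

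**What to change.** Add the note the form already uses, "NB. If for a neonate, please use details of mother", to the overseas healthcare and overseas travel fields, and say that for neonates the 12 months are counted back from delivery. Report these answers as maternal exposure, within the neonatal stratum only.

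The cost is a few words in two field descriptions. Staff must consult the maternal record or ask the mother, and some answers will be Unknown. Sample size, trust selection and the other fields do not change. The neonatal results on these two exposures should be presented as largely descriptive, given the few positives expected.

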#### Study population

Patients of any age in critical care in England, in ICUs which provide levels 2 and 3 care for adults, level 3 care for paediatrics, and both high dependency units (HDUs) and critical care for neonates.

The selection of intensive care units as the focus for this survey is due to the unique characteristics of the patients admitted to these wards. These patients are highly vulnerable to infection. Patients in intensive care also often receive multiple courses of antibiotics, which has been identified as a risk factor for the acquisition of a CRO. The patient mix on these wards also means they often represent both surgical and medical specialities, which may give us wider insight into the true burden of both infection and colonisation with CPE.

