weeks prior to the date of interest?	the four weeks prior to the date of interest	No Unknown
If yes, which?	Carbapenems	Multiselect drop-down Doripenem Ertapenem Faropenem
		Imipenem
		Imipenem with cilastin Imipenem with cilastin and relebactam
		Meropenem  Meropenem/vaborabactam
*Has the patient received carbapenems in the one year prior to the date of interest, but not in the four weeks prior?		Single select drop-down: Yes No Unknown
If yes, which	Carbapenems	Multiselect drop-down
*Has the patient received 3rd generation cephalosporins in the four weeks prior to the date of interest?		Single select drop-down: Yes No Unknown
If yes, which	3rd generation cephalosporins	Multiselect drop-down
*Has the patient received 3rd generation cephalosporins in the one year prior to the date of interest, but not in the four weeks prior		Single select drop-down: Yes No Unknown
If yes, which	3rd generation cephalosporins	Multiselect drop-down
*Antimicrobials prescribed and taken on the date of interest	Indicate if the patient has received at least one	Single select drop-down:

	systemic antibiotic on the date of interest (given or planned treatment, including intermittent treatments, e.g. alternate day or medical prophylaxis). For surgical prophylaxis, check whether any surgical prophylaxis was given in the 24 hours before 8 a.m. on the day of the survey. If "yes", collect antibiotic data.	Yes No Unknown
Please select the number of antimicrobials taken		Single select drop-down:  1  2  3  4  5
*Antimicrobial name 1-5  NOTE: Field repeated up to 5 times depending on the specified number of antimicrobials taken	Select which antimicrobial	Single-select dropdown list of antimicrobials.
*Antimicrobial indication 1-5  NOTE: Field repeated up to 5 times depending on the specified number of antimicrobials taken	Please give indication for this/these antimicrobial(s)	CI = treatment of community-acquired infection LI = treatment of infection acquired in long-term care facility (e.g. nursing home) HI = treatment for acute hospital-acquired infection SP = surgical prophylaxis MP = medical prophylaxis O = other indication UI = unknown indication (confirmed) UNK = unknown or missing information

	T	T
*CPE indication for antimicrobial 1-5  NOTE: Field repeated up to 5 times depending on the specified number of antimicrobials taken	Is this antibiotic prescribed to manage CPE?	Single select drop-down: Yes No Unknown

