Start date for antimicrobial 1-5  NOTE: Field repeated up to 5 times depending on the specified number of antimicrobials taken	Start date of the antibiotic.  If the antibiotic was already given on admission to hospital, provide the date of admission.	DD-MM-YYYY.
Antibiotic stewardship 1-5  NOTE: Field repeated up to 5 times depending on the specified number of antimicrobials taken	Is antibiotic prescription in line with local guidelines	Single select drop-down: Yes No Unknown
*Antimicrobials prior to the date of interest	Indicate how many antimicrobial(s) received since admission to hospital, but stopped prior to the date of interest. If more than 5 antimicrobials were prescribed, please enter details for the most recent 5.	Single select drop-down: Yes No Unknown
*Please select the number of antimicrobials taken this admission, prior to the date of interest	Indicate if antimicrobial(s) received since admission, prior to date of interest	Single select drop-down: 1 2 3 4 5
*Antimicrobial name 1-5 (prior survey)	Select the antimicrobial received since admission, prior to date of interest	Single-select dropdown list of antimicrobials.

		1
NOTE: Field repeated up to 5 times depending on the specified number of antimicrobials taken		
*Indication for antimicrobial 1-5 (before date of interest)  NOTE: Field repeated up to 5 times depending on the specified number of antimicrobials taken	Please give indication for this/these antimicrobial (s)	CI = treatment of community-acquired infection LI = treatment of infection acquired in long-term care facility (e.g. nursing home) HI = treatment for acute hospital-acquired infection SP = surgical prophylaxis MP = medical prophylaxis O = other indication UI = unknown indication (confirmed) UNK = unknown or missing information
*CPE indication for antimicrobial 1-5 (before date of interest)	Is this antimicrobial prescribed to manage CPE?	Single select drop-down: Yes No Unknown
NOTE: Field repeated up to 5 times depending on the specified number of antimicrobials taken		
Start date for antimicrobial 1-5 (before date of interest)	Start date of the antimicrobial. If the antimicrobial was already	DD-MM-YYYY
NOTE: Field repeated up to 5 times depending on the specified number of antimicrobials taken	given on admission to hospital, provide the date of admission.	
Antibiotic stewardship 1-5 (before date of interest)	Is antimicrobial prescription in line with local guidelines	Single select drop-down: Yes

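### The count of antimicrobials stopped before the date of interest ends at five, so patients with more than five cannot be identified and some of their earlier agents go unrecorded

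*Protocol*

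**What the plan says.** The relevant fields are in the protocol, Appendix 1, the per-patient data, under Antimicrobials.

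- **Gate item on antimicrobials before the date of interest.** Its description reads "Indicate how many antimicrobial(s) received since admission to hospital, but stopped prior to the date of interest" and continues "If more than 5 antimicrobials were prescribed, please enter details for the most recent 5". The response options beside it are Yes, No and Unknown.
- **Count item.** The mandatory field "Please select the number of antimicrobials taken this admission, prior to the date of interest" is a single select of 1, 2, 3, 4 or 5. Its description asks whether any were received, not how many.
- **Detail items.** The name, indication, CPE indication, start date and stewardship fields each carry the note "Field repeated up to 5 times depending on the specified number of antimicrobials taken".
- **Separate class items.** Carbapenems are asked about in "the four weeks prior to the date of interest" and again for the earlier part of the year ("Has the patient received carbapenems in the one year prior to the date of interest, but not in the four weeks prior"). The form does the same for the other class ("Has the patient received 3rd generation cephalosporins in the four weeks prior to the date of interest", and the earlier part of the year). These are mandatory Yes/No/Unknown items, each followed by a multiselect list of agents.

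Elsewhere, Study population supports the ICU focus partly because these patients "often receive multiple courses of antibiotics, which has been identified as a risk factor" for acquiring a carbapenem-resistant organism. The Objectives include describing antimicrobials prescribed and understanding which antimicrobial use is associated with CPE. Data analysis plans univariable and, if required, multivariable analysis with odds ratios.

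**The concern.** The form foresees patients with more than five stopped antimicrobials but gives no way to record that a patient is one of them. The upper end of the count is the heavily treated group, and repeated antibiotic treatment is one of the protocol's own reasons for studying ICUs.

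There are two consequences. The count is censored at five. And for an agent outside the two separately asked classes, absence from the list of five can mean that it was not given or that it was pushed out by later agents. Because 5 is ambiguous, an analyst cannot tell which patients have incomplete lists.

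**Working it through.** **1. The rows side by side.**

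| Field | Description asks | Response allows |
|---|---|---|
| Antimicrobials before the date of interest | how many, stopped before that date | Yes / No / Unknown |
| Number taken this admission before that date | whether any were received | 1 / 2 / 3 / 4 / 5 |
| Name, indication and other details | one entry per agent | at most 5 entries |

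In the first two rows the field name agrees with the response, but the descriptions look swapped. The form asks for a total, and neither field can hold a total above five.

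**2. What is lost.** For a patient with k stopped agents, k > 5, the share left unnamed in this block is (k − 5)/k. With illustrative values of k:

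- k = 6: 1/6 = 17%
- k = 8: 3/8 = 38%
- k = 10: 5/10 = 50%

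Any of these that is a carbapenem or 3rd generation cephalosporin given in the previous year is still captured by the separate items.

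**3. Whether it can be recovered.** Information collected says that data obtainable by reliable linkage were already taken out of the questionnaire. The antimicrobial items stayed in, and no linkage is described that would supply the missing agents.

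**4. How many patients are affected.** The protocol does not say. If the number of stopped agents were Poisson, which is purely an assumption, the share above five would be 1.7% at a mean of 2, 8.4% at 3, 21.5% at 4 and 55.4% at 6. A range this wide shows only that the effect cannot be sized from the document.

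**5. The exposure window.** The count runs from hospital admission to the date of interest, not to survey day. That date is the single screen, the first positive screen, or the most recent screen if all were negative. Only never-screened patients use the current date. Among patients screened more than once, the window is therefore set differently for positives and negatives. Truncation need not be equal in the two groups, and its direction cannot be assumed.

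**6. How much the risk-factor analysis could show anyway.** Expected positives at the assumed 1% prevalence, using the largest sample size for each age group:

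- adults: 767 × 0.01 = 7.7
- neonates: 664 × 0.01 = 6.6
- paediatrics: 162 × 0.01 = 1.6

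These totals include the 10% allowance for non-completion, so the realised numbers may be lower.

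**The case against.** The cap is an open rule, not an oversight. The form says which five agents to enter, and limiting staff workload is a stated aim. The classes that the form asks about by name are collected separately without the cap. Agents taken on the date of interest have a further block of up to five. Truncation can occur only among patients coded 5, so a sensitivity analysis could treat the unnamed agents of that group as unknown. With so few expected positives, odds ratios for other agents will be very imprecise with or without the cap. All of this stands, and it keeps the point minor. The sensitivity analysis is only a partial answer, though, because it also discards complete information from patients with exactly five.

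Three stronger readings are tempting and are not supported:

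- **A reader might infer that earlier agents are recorded as never received.** The form has no agent-by-agent yes/no grid, and agents beyond five are simply not entered. They become unexposed only if an analyst codes absence that way, which the protocol does not say.
- **A reader might infer that the ceiling distorts a planned odds ratio per additional antimicrobial.** Data analysis names no such term. Used as any/none, or as categories with five or more at the top, the count is not distorted.
- **A reader might infer that the loss is large in long-stay patients.** The window closes at the date of interest. A long-stay patient whose relevant screen was taken on admission has almost no window.

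An uncapped count would also still be a number of antimicrobials, not of courses, so it only approximates the risk factor cited in Study population.

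**Conclusion.** The point holds as a small flaw in the data-collection form. The count of stopped antimicrobials is top-coded at five. Earlier agents outside the two separately captured classes are unrecorded in patients above five, and those patients cannot be told from patients with exactly five. This rests on the form as printed and on no linkage restoring the missing agents.

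The effect bears on the descriptive and risk-factor objectives only. Its size is probably small and cannot be computed, since the share of patients above five is not given. The prevalence estimates and the sample sizes do not depend on this field. The change is worth making because it costs almost nothing and makes the truncated patients identifiable.

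**What to change.** - Change the response for the count to an integer with no ceiling, or add an option for more than five. The integer keeps more information; the extra option is enough to identify truncated patients.
- Keep the five detailed entries and the rule on which agents to enter.
- Swap the descriptions of the two rows, so that the gate item asks whether any were received and the count item asks how many.
- In agent-specific analyses, treat agents not named as unknown, not as unexposed, when the count exceeds five.
- If the form can no longer be changed, report the top category as five or more, and apply the unknown coding to everyone in it as a sensitivity analysis.

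The cost is one response type and two corrected descriptions. Staff would have to count beyond five for a few patients, with no extra detail to enter.
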